# 19 STATISTICAL METHODS AND CONSIDERATIONS

# 19.1 Sample Size

Below is the original estimate for the 95% upper bound of the Pearl Index for the Mona Lisa Cu IUD arm if we had randomized 800 subjects to that treatment. Since this protocol has been amended to randomize approximately 880 Mona Lisa Cu IUD subjects, the estimated 95% upper bound of the Pearl Index would be slightly lower due to the larger sample size. In addition, the power to detect differences in 12-month IUD continuations rates will be slightly higher than the original power presented below.

Randomizing 800 women to the Mona Lisa Cu IUD will provide approximately 17,700 cycles for the primary efficacy analysis among women under 36 years old at time of enrollment,

assuming 13 cycles of use per year with 84.3% evaluable cycles, an exponential discontinuation rate of 0.2 (i.e., approximately 20% per year), and 37 months of prescribed follow-up per woman. Based on this enrollment total and follow-up rate, the upper bound of the Pearl Index (pregnancies per 100 women-years of follow-up) would be approximately 1.0 if 6 pregnancies were observed (see table).

Table 09: Expected Pearl Index (pregnancies per 100 women-years of follow-up) among women under 36 years old at time of enrollment and 95% CI for Pearl Index as a function of observed number of pregnancies, assuming 800 women are randomized to Mona Lisa Cu IUD and 51.2% method continuation at month 37

Observed pregnancies	Pearl Index	95% CI
0	0.0	0.0-0.3
1	0.1	0.0-0.4
2	0.1	0.0-0.5
3	0.2	0.0-0.6
4	0.3	0.1-0.8
5	0.4	0.1-0.9
6	0.4	0.2-1.0

In terms of estimating and comparing standard 12-month IUD continuation rates, the study will achieve approximately 87% power to detect a 10% greater 12-month continuation rate for the Mona Lisa Cu IUD using a two-sided  $\alpha$ =0.05 level log-rank test, assuming the 12-month probability of continuation for ParaGard is 70% and allowing for up to 5% of women lost to follow-up.

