The proportions of subjects experiencing any other side effects will be calculated with corresponding exact confidence intervals for each group, and compared the difference between groups by Fisher's exact tests or the Cochran-Mantel-Haenszel tests. Generalized linear model approaches for repeated occurrence side effect outcomes might be used to further assess the differences in the incidence of adverse events between study groups.

Overall satisfaction with the method will be summarized and compared between groups at the final study visit using two-sided Mantel-Haenszel chi-square tests. Similarly, the same statistical analysis methods will be used to describe ease of product insertion between groups. Changes in pain with and shortly after insertion from baseline will be described by the summary statistics (mean, median, inter-quartile, etc.) of visual analog scale measurements. The Mann-Whitney test or the analysis of variance method will be used to compare the changes in pain between groups.

For all secondary objectives, comparisons between groups will be made using two-sided 0.05 level significance tests, without adjustment for multiple comparisons.

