7.6.1 Exiting the trial before attempting IUD insertion

The ITT Population will be used for estimating the incidence of exiting the trial before attempting an IUD insertion. Reasons for exiting the trial before attempting IUD insertion include:

- Could not sound the uterus
- Shallow uterine depth (less than 5.5cm)
- Medical contraindication discovered post-randomization but before IUD insertion attempt

The frequency and the percentage of women who exited the trial for different reasons before IUD insertion will be tabulated by treatment group and by study site. The proportions of participants experiencing these events will be calculated with corresponding exact confidence intervals for each group, and the difference between the groups will be compared using the Cochran-Mantel-Haenszel tests.

7.6.2 IUD successful insertion, failed IUD insertion, and incident adverse events during the insertion process

The Treated Population will be used for evaluating the incidence of successful IUD insertion and incident adverse events (e.g., perforation) occurred during the insertion process. The frequency and the percentage of women who experienced IUD placed successfully at the first attempt, at the second attempt, and incident adverse events occurred during the insertion process will be tabulated by treatment group and by study site. The proportions of participants experiencing these events will be calculated with corresponding exact confidence intervals for each group, and the difference between the groups will be compared using the Cochran-Mantel-Haenszel tests.

7.6.3 IUD expulsions, incident adverse events, and other events after a successful IUD insertion

The User Population will be used for analysis of IUD expulsions (complete and partial), incident adverse events, and other events. For each adverse effect (e.g., PID or uterine perforation), two measure units will be used in this analysis: 1) number of participants experiencing at least one adverse effect and 2) number of the AE reporting during the study. First, the proportions of participants experiencing the AE will be calculated using exact confidence intervals for each group and compared between groups using Fisher's exact tests or the Cochran-Mantel-Haenszel tests. Secondly, generalized linear models with GEE for repeated AE outcomes will be used to further explore the differences in the incidence of AEs between study groups.

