Since participants with longer study duration will have more chance to experience adverse effects, the analysis will control for duration since insertion. Note that if the duration in study depends on adverse effects, then the drop out will be non-ignorable. Supporting stratified analyses by study duration or joint modeling of adverse effects and study duration will be considered as sensitivity analyses (Tsiatis and Davidian, 2004).

All expulsions (partial or complete) and accidental self-removals/dislodgements of the IUD will be examined in relationship to type of menstrual hygiene product used by the participant. Participants may use a variety of products over the course of the study. The mutually exclusive categories for analysis will include the following: Any cup use (exclusive cup use or cup use plus any other hygiene product), tampon use (no cup use but tampons used exclusively or tampon use plus other hygiene products), pad (no cup use, no tampon use, but pads used perhaps with some products other than tampons), other products (no cup use, no tampon use, no pad use). A sub-analysis will examine if the self-removal/dislodgement was known to occur during manipulation of the hygiene product. Chi-square tests and/or Fisher's exact tests will be used to examine these associations by IUD group. The proportions of participants with expulsions will be calculated using exact confidence intervals for each type of menstrual hygiene product in each group. Cochran-Mantel-Haenszel tests will be used as appropriate to compare IUD groups.

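### SAP 7.6.3 tests whole-study AE proportions by Fisher or CMH, which do not allow for unequal time at risk; if continuation differs, common AEs spread over follow-up are biased against the longer-used device

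*SAP*

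**What the plan says.** SAP 7.6.3 covers expulsions, AEs and other events in the User Population. Its first between-arm analysis is this: "the proportions of participants experiencing the AE will be calculated using exact confidence intervals for each group and compared between groups", with Fisher's exact or CMH tests. Protocol 19.2.2 has the same approach for other side effects: "The proportions of subjects experiencing any other side effects will be calculated with corresponding exact confidence intervals for each group", again followed by Fisher or CMH. A second analysis follows: "generalized linear models with GEE for repeated AE outcomes will be used to further explore the differences in the incidence of AEs". No person-time term is named for it.

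The next paragraph of 7.6.3 raises unequal follow-up itself: "Since participants with longer study duration will have more chance to experience adverse effects, the analysis will control for duration since insertion". It warns that dropout is non-ignorable if duration depends on adverse effects, and adds: "Supporting stratified analyses by study duration or joint modeling of adverse effects and study duration will be considered as sensitivity analyses".

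Three other places matter:

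- **Length of follow-up.** SAP 1 ends participation at 37 months, or earlier at removal or expulsion. Protocol 12.1 ends AE reporting at Call 4, 17 days (+3) after removal.
- **Continuation.** Protocol 19.1 powers the study for a 10-point gain in 12-month continuation, "assuming the 12-month probability of continuation for ParaGard is 70"%.
- **Expulsion.** SAP 7.4.1 lists complete and partial expulsion as discontinuation reasons. SAP 7.4.2 applies Kaplan-Meier and log-rank methods to each reason.

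**The concern.** The proportion of women who ever report an AE depends on the AE hazard and on how long each woman is observed. Observation stops soon after removal, and continuation is an endpoint on which the arms may differ. If they do, the arm with longer use shows a higher proportion even when the hazards are equal. If the Mini does better on continuation, the error goes against the Mini.

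The promise to control for duration does not settle this. Fisher's test has no place for a duration term. CMH could include one only by stratifying on observed duration, the first of the two sensitivity options named. Observed duration arises after randomisation, and AEs can shorten it: bleeding and pain are listed removal reasons in SAP 7.4.1. Conditioning on it can therefore replace one bias with another. As written, the method of control would be chosen after the data are seen.

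**Working it through.** **1. The plan's continuation scenario.** Inputs from Protocol 19.1: ParaGard 70% at 12 months, Mini 10 points higher, 800 vs 200 women, 5% lost, two-sided 0.05.

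- Hazard ratio: ln 0.8 / ln 0.7 = 0.626.
- Events: (800 × 0.2 + 200 × 0.3) × 0.95 = 209.
- Freedman's formula for 4:1 allocation: z = √(209 × 4) × (1 − 0.626) / (1 + 4 × 0.626) = 3.09.
- Power: Φ(3.09 − 1.96) = 87%, the stated figure.

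This supports reading the alternative as 80% vs 70%. A simulated log-rank test gives 84%; that difference is not pursued here.

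**2. Time at risk.** Take constant removal hazards r = −ln 0.8 = 0.223 and −ln 0.7 = 0.357 per year, and T = 37/12 years. Mean time in use is (1 − e^(−rT))/r.

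- Mini: 2.23 years.
- ParaGard: 1.87 years (ratio 1.19).
- ParaGard, if the arms differ only in year 1: 2.01 years (ratio 1.11).

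**3. Proportion with an AE when the AE hazard h is equal in both arms.** If AEs are independent of removal, P = h/(h + r) × (1 − e^(−(h + r)T)). At h = 0.2 per year:

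- Mini: 0.2/0.423 × (1 − e^(−1.305)) = 34.4%.
- ParaGard: 0.2/0.557 × (1 − e^(−1.716)) = 29.5%.

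**4. Fisher's test at 880 vs 220 (Protocol 4.1), two-sided 0.05.**

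| Assumed AE hazard per year | Mini | ParaGard | Ratio | False rejection, gap persists to month 37 |
|---|---|---|---|---|
| 0.02 | 4.3% | 3.6% | 1.19 | 4–5% |
| 0.05 | 10.4% | 8.8% | 1.19 | 7–9% |
| 0.1 | 19.5% | 16.5% | 1.18 | about 14% |
| 0.2 | 34.4% | 29.5% | 1.17 | about 27% |
| 0.4 | 54.8% | 47.7% | 1.15 | about 46% |

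The rates are simulated. Exact enumeration of the two binomials at the last three hazards gives 15.2%, 27.2% and 45.9%, so simulation error is about a point. From 0.1 per year upward, almost every rejection is against the Mini. If the arms differ only in year 1, the rate at 0.2 per year falls to about 13% (exact 13.7%).

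**5. Where the effect is small.**

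- Events confined to the first 3 months: the ratio is at most about 1.02 (for example 9.7% vs 9.6%).
- Expulsion, using the ParaGard label rates of 5.7, 2.5 and 1.6 per 100 in years 1 to 3 (Protocol Appendix 7) for both arms: 8.2% vs 7.2%. Fisher rejects 5.6% of the time, against 4.2% with equal proportions.

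**6. Alternatives.** Log-rank on time to first AE rejected 3–6% of the time across the scenarios run, including those where AEs prompt removal. One possible form of duration control, logistic regression with total duration as a covariate, rejected:

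- 4–6% when AEs never led to removal;
- 8–20% when 30% of affected women had the device removed (hazards 0.2–0.4 per year);
- 18–41% when 60% did.

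The SAP does not specify that model, so these last figures only illustrate the mechanism.

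**The case against.** The strongest reply is that the SAP already sees the problem. A reader might infer from the Fisher sentence alone that the plan ignores unequal follow-up. It does not: the following paragraph commits to duration control and holds joint modelling in reserve. Duration since insertion could also be meant as a time term in the repeated-AE model, which would be sensible. That stands as a defence of intent, but no method is named, and none can be attached to Fisher's test.

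A reader might also infer that expulsion lacks a proper analysis. The by-reason analysis in SAP 7.4.2 and Protocol 19.2.2 already supplies one, and the bias for expulsion is small.

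Third, the examples named in 7.6.3, pelvic inflammatory disease and perforation, are uncommon. Protocol 21.3.1 puts the first at about 1% in the three weeks after insertion and the second at 1 in 1000. For such events Fisher is close to nominal. Bleeding and pain also have separate diary and per-visit analyses (SAP 7.5.2 and 7.6.7) with provisions for informative censoring. This limits the point to common AEs spread over follow-up. Protocol 21.3.1 does quote 20% to 50% of users for bleeding changes and painful menses, so proportions of that size are plausible, but it does not give their timing over three years.

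Finally, log-rank is not a complete cure. With a shared frailty linking AE and removal risk (assumed variance 0.5–2), it rejected 5–9% of the time. That is far better than Fisher for common AEs, but it is a reason to keep joint modelling.

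**Conclusion.** The point holds for common AEs spread over follow-up, if continuation differs between arms. Under the powered alternative extended to month 37, false rejection is about 14%, 27% and 46% at hazards of 0.1, 0.2 and 0.4 per year. At 0.2 per year it is about 13% if the arms separate only in year 1. It is negligible for rare or early AEs and small for expulsion.

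These sizes rest on assumptions outside the documents: the AE hazards, constant removal hazards, and AEs independent of removal.

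Two stronger readings are not supported. One is that the plan expects longer use of the Mini, so the Mini will look more harmful. In fact 80% vs 70% is the alternative for a two-sided test, not a forecast, and with equal continuation this bias disappears. The other is that the flaw threatens the trial's main conclusion. The primary objective is non-comparative, these are secondary comparisons without multiplicity adjustment or a decision rule, and person-years by group are tabulated under SAP 7.1. It should be fixed, but it is not critical.

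**What to change.** In SAP 7.6.3:

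- Make time from insertion to first AE, censored at the end of the AE reporting window, the between-arm comparison (log-rank or Cox), with cumulative incidence at 12 and 36 months.
- State that control for duration in the repeated-AE GEE means log(time at risk) as an offset.
- Keep crude n (%) with exact intervals as description only.
- Drop the stratification by total study duration.
- Keep joint modelling as the sensitivity analysis for informative removal.
- Cross-refer expulsion to the existing SAP 7.4.2 analysis.

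Events during insertion (7.6.2) can stay as proportions. Protocol 19.2 allows departures from its summary to be documented in the SAP, so the change from 19.2.2 can be recorded there.

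The cost is a few sentences and standard programming. AE dates (Protocol 12.1) and removal information (Protocol Appendix 1) are already collected, and SAP 7.4.2 already uses Kaplan-Meier, log-rank and Cox methods.

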7.6.4 Pain on insertion day and pain in first 7 days post insertion

The level of pain for participants will be measured by visual analog scale at 9 time points:

- At baseline (after speculum placement but before IUD insertion)
- Immediately post IUD insertion
- 10 minutes after insertion
- Daily from Day 1 to Day 6 post IUD insertion (these last six measures are completed by the participant at home).

Thus, the Treated Population will be used for the baseline (it is anticipated that unsuccessful insertions will have a pain measurement that describes the level of pain from the attempted procedure). The User Population will include all 9 measures. The level of pain will be summarized by means, standard deviations, medians, interquartile ranges, minimum and maximum by each time point, site and study group. Changes in pain from baseline will be described by the summary statistics (mean, median, inter-quartile, etc.). T-tests or the Mann-Whitney tests will be used to compare the changes in pain between groups at each time point of post insertion. A generalized linear model will be used to evaluate the time trend of changes in pain between groups and to compare changes in pain between groups across all post insertion time points.

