5.3. Treated Population

The Treated Population is a subset of ITT Population and includes only participants who advanced to uterine sounding, had their uterus successfully measured, and then underwent an attempted IUD insertion procedure. Inadequate uterine depth (at least 5.5cm) and/or medical contraindication (such as mucopurulent discharge discovered before/during/after sounding) are examples of situations that exclude participants from the Treated Population. Participants who received the incorrect IUD are included in this population and analyzed according to the treatment they actually received. This analysis population will mainly be used for evaluating insertion results and safety and other secondary endpoints observed during the insertion process. Participants' baseline characteristics will be analyzed only if more than 5% of the ITT Population are excluded from the Treated Population.

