5.4. User Population

The User Population is a subset of Treated Population who had a successful IUD insertion. It includes participants who leave the clinic with the IUD in situ as well as those who have the product removed before leaving the clinic and exit from the study. This analysis population will mainly be used for analyzing discontinuation and safety and other secondary endpoints after a successful IUD insertion.

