5.7. Lost to Follow-up Population

Lost to Follow-up Population is a subset of User Population who have the following experiences:

- left the clinic with the IUD in situ and
- had no documented IUD removal and
- whose last known use of the IUD was earlier than 37 months after IUD placement.

A subset of the Lost to Follow-up Population that has no follow-up data whatsoever is referred to as "Completely" Lost to Follow-up. Participants' baseline characteristics will be analyzed if more than 5% of the User Population are excluded from the Lost to Follow-up Population.

The following table summarizes various analyses conducted on each analysis population.

Table 1: Analyses performed on each analysis population

	Analysis						
Population				Safety and other			
1 opulation			IUD	secondary			
	Baseline	Efficacy	Discontinuation	endpoint			
Screened							
ITT	✓			✓			
Treated	√*			√ ‡			
User	✓		✓	✓			
Per protocol	✓		√ ***	√ ***			
Efficacy Analysis	✓	✓					
Lost to Follow-up	✓ **						

^{*} Analysis will be performed if > 5% of ITT Population is excluded.

^{**} Analysis will be performed if > 5% of User Population is lost to follow-up.

^{****}Analysis will be performed if > 5% of User Population is excluded.

[‡] Analysis will be performed for safety and other secondary endpoints observed during the insertion process.

The following table summarizes various study participant status included in each analysis population.

Table 2: Study participant status included in each analysis population

	Population						
Study participant status	Screened	ITT	Treated	User	Per Protocol	Efficacy	LTF
Early situations							I
Screen failures	✓						
Eligible but not enrolled	✓						
Enrolled	✓						
Protocol violation on enrollment	✓						
Post-randomization situations		•					•
Medical contraindication*		✓					
No successful sounding of the		✓					
uterus							
Uterine depth < 5.5cm		✓					
No IUD placement attempt**		✓					
Randomization errors (as		✓					
assigned)							
Randomization errors (as			✓	✓		✓	✓
treated)							
IUD placement attempts							
Attempted but failed IUD placement		✓	✓				
Successful IUD placement but		√	√	√			
immediate removal per							
request by participant							
Successful IUD placement		√	✓	√	√	√	√
and leaves clinic with IUD in							
situ							

^{*} e.g., discovering mucopurulent cervical discharge before/during/after sounding the uterus ** IUD placement attempt is defined as handling the product and attempting to place it

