7.6. Analysis of Other Secondary Endpoints and Safety Data

The ITT population will be used for analyses involving pre-IUD insertion events, and the Treated Population will be used for the safety and other secondary endpoints analyses during the insertion process, and the User Population will be used for the safety and other secondary endpoints analyses after a successful IUD insertion. Descriptive statistics will be calculated by pooling data across

sites. In addition, a supporting analysis will be performed using the Per Protocol Populations if more than 5% of participants in the User Population are excluded.

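### SAP 7.6.4 conflicts with the SAP's own population rules: read literally, women whose insertion finally failed enter no between-arm comparison of insertion pain

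*SAP*

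**What the plan says.** Pain with and shortly after insertion is a secondary endpoint to be compared between devices (SAP 2.2 and 3.2). SAP 7.6.4 lists nine visual analogue scores: baseline, immediately after insertion, 10 minutes after, and Days 1 to 6 at home. On populations it says "Thus, the Treated Population will be used for the baseline", adding in parentheses that "it is anticipated that unsuccessful insertions will have a pain measurement that describes the level of pain from the attempted procedure". The next sentence is "The User Population will include all 9 measures". The between-group tests compare change from baseline at each post-insertion time point, and a generalised linear model compares changes across all of those time points.

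The populations are defined in SAP Section 5:

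- User Population (5.4): "The User Population is a subset of Treated Population who had a successful IUD insertion".
- Treated Population (5.3): women who "had their uterus successfully measured, and then underwent an attempted IUD insertion procedure".
- Table 2: the row "Attempted but failed IUD placement" is ticked for ITT and Treated, but not for User.

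The general rule in SAP 7.6 is that "the Treated Population will be used for the safety and other secondary endpoints analyses during the insertion process". The Table 1 footnote to the Treated row says the same: "Analysis will be performed for safety and other secondary endpoints observed during the insertion process". SAP 7.6.5 applies the rule and assesses ease of insertion in the Treated Population.

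**The concern.** Pain measured immediately and 10 minutes after an insertion attempt belongs to the insertion process. The general rule puts it in the Treated Population; the specific section, as worded, puts every post-baseline score in the User Population. Two analysts could follow the same SAP and compare different sets of women.

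Under the literal reading, pain is compared only among women whose insertion succeeded. Success is determined after randomisation, may depend on the device, and is itself a compared endpoint. Ease of insertion and insertion pain, which arise from the same procedure, would also be reported on different women.

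The Protocol makes a gap in failure rates plausible without giving one. The control device is 32 mm wide, the background section cites a mean cavity width of 27 mm in nulliparous women, and about 80% of recruits are to be nulliparous. If the larger device failed more often and failed attempts hurt more, leaving out the failures would understate pain in the control arm.

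**Working it through.** The plan states no power, SD, expected difference or failure rate for the pain endpoint, so there is no figure to reproduce. The main check is textual; the arithmetic after it is for scale only.

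**Text.**

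1. SAP 7.6.4 attaches the Treated Population to the baseline score alone.
2. It attaches the User Population to all nine scores. By 5.4 and Table 2, that population excludes final failures.
3. Every between-group pain test uses change from baseline, so each woman needs a post-baseline score within the named population.
4. It follows that final failures contribute to the baseline summary but to no comparison.
5. A score describing pain from the attempted procedure cannot be a baseline score, because baseline is taken after speculum placement and before sounding (Protocol Table 03). The SAP therefore expects a post-baseline score and gives it no analysis.
6. Steps 1 to 4 contradict SAP 5.3, 7.6 and the Table 1 footnote, and differ from 7.6.5.

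**Scale.** Let f be the share of attempts that finally fail in an arm, and D the mean excess pain in failed over successful attempts, taken as equal in both arms. Then

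mean(Treated) = (1 − f) × mean(User) + f × [mean(User) + D] = mean(User) + f × D,

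so moving from User to Treated shifts the control-minus-test difference by (f_control − f_test) × D.

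Assumed inputs, none of them from the documents: f_test 1-3%, f_control 3-10%, D 15-25 mm, SD 28 mm. From Protocol 4.1: about 880 test and 220 control women.

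| Failure, test v control | Gap | Shift, D = 15 mm | Shift, D = 25 mm |
|---|---|---|---|
| 3% v 3% | 0 points | 0 | 0 |
| 1% v 3% | 2 points | 0.30 mm | 0.50 mm |
| 3% v 10% | 7 points | 1.05 mm | 1.75 mm |
| 1% v 10% | 9 points | 1.35 mm | 2.25 mm |

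The full range is 0 to 2.25 mm.

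Standard error of the difference = 28 × √(1/880 + 1/220) = 28 × 0.0754 = 2.11 mm. The largest shift is 2.25 / 2.11 = 1.07 standard errors.

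Difference detectable with 80% power at two-sided 0.05 = (1.960 + 0.842) × SD × 0.0754, which is about 4.2, 5.3 and 6.3 mm for SDs of 20, 25 and 30 mm.

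Women affected: 880 × 1-3% is about 9 to 26 in the test arm, and 220 × 3-10% is about 7 to 22 in the control arm.

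The formula applies to means. The SAP also allows the Mann-Whitney test, for which the effect would have to be judged on ranks.

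**The case against.** The best reply is that 7.6.4 is garbled rather than wrong. It never says that failed attempts are left out of the post-insertion scores. Its parenthesis makes sense only if the Treated Population was meant to bring failed attempts into insertion-day pain, which would agree with 7.6. The sentence on nine measures may mean only that Users alone can supply all nine, since women with failed insertions are discontinued (Protocol 9.4 and 15.1). This stands as a possible intention. A reader might infer that the SAP deliberately discards these scores, and the text does not support that. It does support a contradiction that has to be resolved before analysis.

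Other points carry weight:

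- A reader might infer that all of the hardest procedures are lost. They are not: a woman whose first attempt failed and whose second succeeded is in the User Population. Only final failures leave.
- A reader might infer that control-arm pain is certainly understated. The notes to Protocol 11.1.2 bar anaesthesia at the first attempt but permit cervical anaesthesia at a second. That could reduce the excess pain recorded after a final failure, so the direction is uncertain.
- Both clinic scores may not exist for failed attempts. Protocol 10.3.4 and the clinic form in Appendix 5 time them from IUD placement, with no instruction for a failure, and the SAP anticipates one measurement.
- Failures are not hidden. SAP 7.6.2 analyses them in the Treated Population, and 7.6.5 does the same for ease of insertion.
- The Treated Population is itself selected after randomisation. It requires successful sounding and an attempt, the inserting clinician knows the device (Protocol 9.2), and women are analysed as treated. Using it reduces the selection but does not remove it.

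None of this defends restricting the immediate and 10-minute comparisons to successful insertions.

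**Conclusion.** The inconsistency is real. Taken literally, SAP 7.6.4 makes the comparison of insertion pain conditional on insertion success, against the SAP's own rule for insertion-process endpoints.

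The size and direction of any resulting bias cannot be determined from the documents. The 0 to 2.25 mm range rests wholly on assumed failure rates and an assumed excess common to both arms. It is zero when failure rates are equal and would shrink if anaesthesia at a second attempt lowered the excess. Even its upper end is about one standard error and below what the trial could detect. It would, however, be systematic, and it would not diminish with more women.

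The point is minor: a secondary endpoint tested without multiplicity adjustment. The Day 1-6 home scores are rightly kept to the User Population, because women with a failed insertion have no device and leave the study.

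**What to change.** State in SAP 7.6.4 that:

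- the immediate and 10-minute scores, and their changes from baseline, are compared in the Treated Population, using every available score from failed attempts;
- where there were two attempts, a named attempt supplies the score, chosen before the data are examined;
- the User Population is kept for the Day 1-6 home scores and as a supportive analysis of the two clinic scores.

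Report by arm how many failed attempts have each clinic score, so that a reader can see how complete the comparison is.

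The cost is a few sentences in the SAP. There are two limits. Some failed attempts may lack one or both scores, and the documents do not show that scores were to be collected from every one. The Treated Population also still depends on successful sounding and an attempt after randomisation, which the report should acknowledge.
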